9.3.2 Documentation and notification

9.3.2.1 Documentation and reporting of Adverse Events / Reactions

The principal investigator shall:

- a) record in the CRF every **adverse event** and adverse reaction, together with an assessment,
- b) adverse event reporting will extend from signing of informed consent until the final study visit.
- c) report to the sponsor, without unjustified delay, all serious adverse events and reactions; this information shall be promptly followed by detailed written reports,
- d) supply the sponsor, upon sponsor's request, with any additional information related to the safety reporting of a particular event.

All AEs, regardless of the relationship to the investigational product, will be recorded in the CRF.

All AE reports should contain: **a brief description of the event, localization, date and time of onset, duration (hours or days), intensity of symptoms (severity), treatment required, relationship with IP and protocol procedure, action taken with the IP, outcome, date and time of resolution and whether the event is classified as serious.**

LABORATOIRES THEA	Protocol # LT2769-001/ 17E1044	Final Version 2.0 Date: 13/11/2017	Confidential Page 55/75
-------------------	--------------------------------	---------------------------------------	----------------------------

All AEs experienced by a patient, irrespective of the suspected causality, will be monitored until the event has resolved, any abnormal laboratory values have returned to baseline or stabilised at a level acceptable to the investigator and Medical expert, until there is a satisfactory explanation for the changes observed, or until the patient is lost to follow-up.

9.3.2.2 Documentation and reporting of Serious Adverse Event by the investigator to the sponsor

In case of Serious Adverse Event, the Investigator must:

1. Complete the relevant CRF pages and the SAE form with all available initial information

Immediately scan and send out the completed SAE form to the

[contact] whilst copying the field CRA of the CRO.

If it is not possible, please fax this SAE form to: **[contact]**

2. **Within 24 hours**, send the completed original SAE form duly completed to the following address by mail:

GlobalSafety and MedInfo Department

Laboratoires théa

[name]

[name]

The initial report must be as accurate as possible, including details of the current illness, an assessment of the causal relationship between the event and the IP. Additional follow-up reports, must be send back to Laboratoires Théa within 24 hours upon receipt of follow-up information query.

In addition, the following information have to be recorded in the appropriate sections of the CRF:

- Demography
- Medical and surgical history
- Previous and concomitant medication
- Study medication administration record

LABORATOIRES THEA	Protocol # LT2769-001/ 17E1044	Final Version 2.0 Date: 13/11/2017	Confidential Page 56/75
-------------------	--------------------------------	---------------------------------------	----------------------------

The Investigator is responsible for ensuring the follow-up of any patient who experiences an SAE during the study. The Investigator or an appropriate qualified physician must re-examine the patient at regular intervals until completion of the Last Patient Last Visit. Further follow up information will be reported to Laboratoires THÉA.

As for all other study documents, the Investigator will retain a copy of the SAE form for 15 years.

Any SAE occurring **within 1 month after the end of the study** and considered to be related to the IP, and therefore deemed as a possible Serious Adverse Drug reaction, must be reported to the Sponsor

After consultation with Laboratoires THÉA, the Investigator may be required to provide information about certain SAE to the independent ethics committee (IEC) according to the institutional policy.

9.3.2.3 Notification of the SUSAR by the sponsor to the NCA

All suspected adverse reaction related to an investigational product which occur in the concerned trial, and that are both unexpected and serious (SUSARs) must be reported to the Competent Authorities and Independent Ethics Committee:

- as soon as possible but not later than 7 calendar days in case of fatal or life threatening SUSARs,
- as soon as possible but not later than 15 calendar days for all other SUSARs.

The Sponsor must declare to the Competent Authorities and Independent Ethics Committee, with a follow-up report, any complementary relevant information concerning unexpected serious adverse effects. In case of fatal or life threatening SUSARs, this complementary information is notified in a new delay of 8 days from the delay of 7 days mentioned above, and a new delay of 15 days for all others SUSARs.

9.3.2.4 Sponsor's annual report to the Competent Authority and to the Ethics Committee

Once per year for the duration of the research or on request the sponsor transmits a safety report with all the available safety information to the CA and the EC. This report includes notably, the list of all the suspected serious adverse reactions and an analysis of the information regarding the safety of individuals participating in the research.

9.3.2.5 Process for reporting a pregnancy

This is the same process as serious adverse event reporting.

The occurrence of a pregnancy (reported or diagnosed) must be reported by the Investigator to the Sponsor as an SAE from the signature of the informed consent form, within 24 hours.

9.4 Adverse events follow-up

The adverse events which are not related to the tested product(s) or to the protocol are not followed-up. The adverse events/effects susceptible to be in relationship with the tested product(s) or the protocol are followed by the investigator until stabilization or resolution of the symptoms.

If it is required, the investigator can take the decision to prescribe an appropriate treatment to the subject and/or to orientate the subject to an appropriate specialist.

In the frame of this follow-up and according to the investigator's request, some extra visits should be performed by the subject (during the research or after the research termination).

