3.4 Summary of potential benefits and risks for the patients

The literature analysis points out the clinical benefits of the three main ingredients of T2769 in the treatment of DED. Clinical studies on sodium hyaluronate 0.15% (Hyabak®), trehalose 3% (Thealoz®) and the combination of sodium hyaluronate 0.15% and trehalose 3% (Thealoz Duo®) confirmed that these agents are valuable options in the management of DED (*i.e.*, allowing

protection, hydration and lubrication of the eye, and improving ocular symptoms and signs) (Ramothe et al., 2013; Brjesky et al., 2014; Schmidl et al., 2015; Pinto-Bonilla et al., 2015; Chiambaretta et al., 2017). The treatment of dry eye patients with NAAGA 4.9% was also shown to significantly decrease the expression of inflammation markers and to improve ocular symptoms and overall comfort (Brignole-Baudouin et al., 2009).

As regards safety, the combination of sodium hyaluronate 0.15% and trehalose 3% (Thealoz Duo®) is well tolerated and safe for the treatment of DED. In a recent clinical study conducted in DED patients (Chiambaretta et al., 2017), the incidence of ocular AEs was lower for Thealoz Duo® (1 patient, 1.9%) than for the reference product Vismed® (sodium hyaluronate 0.18% eye drops) (7 patients, 13.2%). The ocular AE (moderate viral conjunctivitis) experienced by the patient in the Thealoz Duo® group was not considered to be treatment-related by the investigator. No serious adverse event was reported in this study. For NAAGA (at 4.9%), among the 53 dry eye patients included in the Brignol-Baudouin's study (Brignole-Baudouin et al., 2009), one patient reported worsening of an existing blepharitis (for which the relation to treatment was considered doubtful by the investigator) and another patient reported hyperaemia, burning sensation and lid swelling (considered as possibly related to treatment) in the Naabak® group. No serious adverse event was reported in this study.

Currently, the product information mentions the following side effects for Thealoz Duo® and Naabak® (NAAGA at 4.9%), respectively:

- *"You may have mild eye irritation, although is very unusual"* (Thealoz Duo® IFU, 2015)
- *"Possibility of brief sensation of burning or stinging at instillation"* (Naabak SmPC, 2016)

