6.6.2 Early Study discontinuation

6.6.2.1 Criteria and modalities of premature end of treatment or subject exclusion from the study

The patient may voluntarily withdraw from the study at any time without penalty and for any reason without prejudice to her future medical care (Declaration of Helsinki).

The patient must be withdrawn from the study if, in the opinion of the investigator, there is any situation or condition which puts the patient at significant risk.

The investigator may decide to withdraw a patient for the following reasons:

- Adverse event(s) or Adverse Effect(s) necessitating study discontinuation ,
- Ocular dryness worsening from baseline according to the investigator's judgement and/or ocular examination

- Lack of efficacy: if the patient or the investigator does not feel that the treatment has adequately relieved his/her symptoms,
- Patient's request.
- Other reason.

In case of withdrawal from the study, the investigator will prescribe the best appropriate treatment to the patient.

In all cases, the date and the primary reason for withdrawal, must be recorded on the case report form (CRF) and patient files (source documentation).

If a patient is prematurely withdrawn from the study for any reason, the investigator must make every effort to perform the evaluations described for the Day 42 visit.

The patient discontinued for AE(s) will be followed-up after discontinuation until the event is resolved or considered medically stable by the investigator.

If a patient is lost-to-follow-up, the investigator must do his/her best to contact the patient initially by phone, then by letter, and finally by certified mail. If no response is obtained from the patient, the investigator is encouraged to contact one of the patient's relatives or her general physician. The evidence of these contacts must be recorded in the patient files.

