4.3.18 AE duration

Duration (days) of an AE will be calculated as follows:

(Date of recovery – Date of onset) + 1.

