7.5.3 Individual listing of adverse events

Individual patient data listings of AEs will be performed for AEs, SAEs and drug-related SAEs, separately for ocular and systemic AEs. The following variables will be presented:

- Patient's identifier,
- Gender,
- Age at baseline,
- Investigator's reported term,
- SOC,
- PT,
- Localisation,
- Date / Time of onset,
- Time to onset (days) from the date of the first IP instillation,
- Treatment-emergence,
- Date/Time of recovery / Date of death, if any,
- Duration (days),
- Outcome,
- Frequency and details,
- Severity,
- Action taken regarding the IP,
- Requirement for therapy adjustment/modification,
- Requirement for surgical / medical procedure and details,
- Seriousness,
- Relationship with the IP in the investigator's opinion and details,
- Relationship with protocol procedure and details.

Listings will be sorted by patient's identifier and date of onset.

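### Protocol 9.3.2.1 and 9.4 give opposite follow-up instructions for adverse events judged unrelated, and no text says which prevails (low severity)

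*Protocol*

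**What the plan says.** Several passages of the current protocol govern follow-up of adverse events.

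- **9.3.2.1:** "All AEs experienced by a patient, irrespective of the suspected causality, will be monitored until the event has resolved". The sentence goes on to allow stabilisation, a satisfactory explanation or loss to follow-up as end points. Each report must also give duration and "outcome, date and time of resolution and whether the event is classified as serious". Item (b) of the same section ends adverse event reporting at the final study visit.
- **9.4:** "The adverse events which are not related to the tested product(s) or to the protocol are not followed-up". Its second sentence reserves follow-up to stabilisation or resolution for events that may be related to the product or protocol.
- **9.3.2.2:** "The Investigator is responsible for ensuring the follow-up of any patient who experiences an SAE during the study". No causality condition is attached.
- **6.6.2.1:** "The patient discontinued for AE(s) will be followed-up after discontinuation until the event is resolved or considered medically stable by the investigator". Again there is no causality condition.
- **6.6.2.3:** a patient who leaves early is followed when the exit is due to an adverse *effect*, a different term from the one in 6.6.2.1.
- **9.1.1:** refers the reader to section 9.3 for the handling of adverse events and does not mention 9.4.

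In the SAP, 4.3.18 derives duration from the recovery date ("Duration (days) of an AE will be calculated as follows": recovery minus onset, plus 1). Section 7.5.3 provides that "Individual patient data listings of AEs will be performed for AEs, SAEs and drug-related SAEs, separately for ocular and systemic AEs", with recovery date, duration and outcome among the fields.

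**The concern.** An investigator with a patient whose unrelated event is still open finds an instruction to keep monitoring it in 9.3.2.1 and an instruction not to follow it in 9.4. Either course can be defended from the protocol, and either departs from it. The SAP names three centres, so practice could differ between them. The causality scale in 9.3.1.5 has only two categories, so a doubtful event must be placed on one side or the other, and under 9.4 that label decides whether follow-up stops.

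Two things are at stake. One is the care of the patient with an open event. The other is the completeness of a few descriptive safety fields, in a study whose only secondary objective is safety.

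Section 3.4 illustrates the kind of event affected. In an earlier study of the hyaluronate and trehalose combination, a moderate viral conjunctivitis "was not considered to be treatment-related by the investigator". That was a different product and says nothing about how often such events will occur here. A similar event in this trial, if non-serious and without withdrawal, would be monitored to an end point under 9.3.2.1 and left under 9.4.

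**Working it through.** No power or sample size figure is involved. The check is a comparison of texts and a count of the data items affected.

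**Step 1. Apply each rule to an event judged unrelated.**

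| Type of unrelated event | 9.3.2.1 | 9.4 | Specific rule |
|---|---|---|---|
| Serious | Monitor | Not followed | Follow (9.3.2.2) |
| Led to discontinuation | Monitor | Not followed | Follow (6.6.2.1); 6.6.2.3 says *effect* |
| Non-serious, no withdrawal | Monitor | Not followed | None |

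The instructions conflict in every row. In the first two rows a specific rule can break the tie. In the third nothing does.

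**Step 2. Try to reconcile the two sections.**

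- *Monitoring and follow-up might be different activities.* Monitoring under 9.3.2.1 runs to resolution or loss to follow-up, which is follow-up in substance.
- *9.4 might apply only after the study.* Its last sentence provides for extra visits both during the research and after it ends.
- *9.3 might take precedence through 9.1.1.* That sentence is a pointer. It neither ranks 9.3 above 9.4 nor mentions 9.4, whose title is the one a site would look for on this question.

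None of these removes the conflict.

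**Step 3. Narrow the exposure.** Assume the specific rules for serious events and for withdrawals prevail. What remains is non-serious events, labelled unrelated, that did not cause withdrawal. Adverse events are collected at D14 and again at D42 (9.1.1), so an event that resolves between those visits can be closed at D42. The exposure is therefore mainly events still ongoing at D42, after which no visit is scheduled.

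**Step 4. Count what could be missing.**

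- Report items in 9.3.2.1: description, localisation, onset, duration, intensity, treatment, relationship, action taken, outcome, resolution date, seriousness = 11. Those that depend on follow-up: duration, outcome in its final form, resolution date = 3.
- Fields in the SAP 7.5.3 listings = 21. Those that depend on follow-up: recovery date, duration, final outcome = 3.
- Listings: 3 types (all events, serious, drug-related serious) × 2 (ocular, systemic) = 6. Those that contain non-serious unrelated events: the all-event type × 2 = 2.
- Safety tables 5.1 to 5.26 = 26. Titles naming outcome, recovery date or duration of adverse events = 0.

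**Step 5. Check whether counts change.** Section 9.3.2.1 requires every event to be recorded whatever its relationship to the product. Counts of treatment-emergent events, serious events and events leading to withdrawal rest on that record and not on how long the event was followed.

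**The case against.** The strongest reply is that the protocol already leans towards the fuller rule: 9.1.1 sends the reader to 9.3, and the practical effect is small. Part of this stands. The pointer makes 9.3.2.1 the more likely reading, but it does not cancel a current sentence in 9.4 that says the opposite.

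Three further points are fair and limit the claim.

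- An outcome can still be entered at D42 as ongoing. What may be lost is the *final* outcome, with the recovery date and duration.
- Because 9.3.2.1(b) ends reporting at the final visit, recovery dates after D42 could be absent even if 9.3.2.1 governs. Correcting 9.4 alone would not close the gap.
- The SAP has no rule for duration when the recovery date is absent, but that touches any unresolved event, related ones included. It is a separate matter and not a consequence of 9.4.

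The different term in 6.6.2.3 also matters. Section 6.6.2.1 lists adverse events and adverse effects as distinct grounds for withdrawal, so the withdrawal rule is not stated consistently without regard to causality.

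**Conclusion.** The contradiction is real and lies in current operative text. Its reach is narrow: non-serious events labelled unrelated that did not cause withdrawal, mainly those ongoing at D42. For these the patient may not be followed, and final outcome, recovery date and duration may be missing from 2 of the 6 adverse event listings. This rests on one assumption, that the specific rules for serious events and for withdrawals override 9.4. The documents give no expected number of unrelated events, so no patient count can be given. Severity is low.

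A reader might infer that the safety results as a whole are compromised, or that efficacy is touched. The documents do not support this: all events are recorded whatever their causality, no safety table title refers to the affected fields, and no efficacy endpoint uses them. A reader might also infer that unrelated serious events will go unfollowed. That follows only if 9.4 is allowed to override 9.3.2.2, which no text says.

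**What to change.** Three short edits to the protocol:

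1. **9.4:** replace the first two sentences with the 9.3.2.1 rule, so that every adverse event, whatever its causality label, is followed until resolution, stabilisation, satisfactory explanation or loss to follow-up. The remaining sentences on treatment, referral and extra visits can stay.
2. **6.6.2.3:** change *adverse effect* to *adverse event*, in line with 6.6.2.1.
3. **9.3.2.1(b):** state that the end of reporting at the final visit applies to new events, and that outcomes of events ongoing at that visit are still recorded afterwards.

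The cost is a few sentences and a little more follow-up of non-serious unrelated events, possibly a contact or an extra visit after D42. The main rule is one the sponsor has already written.

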10 DATA HANDLING AND STUDY MONITORING

10.1 Data collection and control

At each visit of the subject, the investigator reports in the source documents the data related to the subject's health state and the safety of the product(s) applied according to the protocol within the study. These data are then reported in the Case Report Form. All data for this study will be recorded on Case Report Forms.

The case report forms will be designed to identify each subject by a subject number and, where appropriate, subject's initials. One Case Report Form must exist for each subject participating in the study. The case report form must be completed legibly, using a black ballpoint pen. Erroneous values and/or text must not be erased. Instead, the error must be crossed out with a single line, the correct value/text added, and the correction signed, initialled and dated by the investigator(s).

The Clinical Research Associate ensures the coherence and the veracity of the data reported in the Case Report Form comparing to the source data and the protocol of the study.

10.2 Clinical monitoring

The monitoring of the study will be done by the CRO DermScan. The monitor has the responsibility to familiarise the Investigator(s) and the centre staff involved in the study with all study procedures if necessary. The monitor has the responsibility of reviewing the ongoing study with the Investigator(s) to verify adherence to the protocol and to deal with data queries as well as any problems that arise during the conduct of the study.

10.2.1 Monitoring visits

10.2.1.1 Initiation visit

Before any patient's enrolment, the CRA and/or the study monitor will conduct an initiation visit in order to familiarise the centre's staff with the study protocol and schedule.

This visit will also be the occasion to review with the centre:

- the Investigator file which should contain:
 - the Protocol of the study,
 - the curriculum vitae of the Investigator,
 - the Authorisation as a clinical centre, if applicable,
 - the insurance certificate,
 - the favourable opinion of the ethic committee,
 - the approval of CA,
 - the Investigator brochure,
 - the financial agreement between all parts,
 - all necessary documents for study follow-up, etc.
- the CRF and the way to complete it,
- the information sheet and consent forms and the way to obtain consent,
- the investigational product,
- the auxiliary treatment
- the study material (pregnancy test, etc.),
- and all other necessary aspects and materials detailed in the study protocol.

10.2.1.2 Monitoring visits

For the duration of the study, monitoring visits may be performed by the CRA in order to check the study efficacy in accordance with the study protocol.

LABORATOIRES THEA	Protocol # LT2769-001/ 17E1044	Final Version 2.0 Date: 13/11/2017	Confidential Page 59/75
-------------------	--------------------------------	---------------------------------------	----------------------------

The Clinical Research Associate ensures the coherence and the veracity of the data reported in the Case Report Form compared to the source data. He/she verifies that the study is performed according to the protocol and that all documentation necessary to ensure a good follow-up of the study is present and well completed.

These visits will also serve to ensure products accountability.

During these visits, the CRA reserves the right to ask for queries resolution, directly in the document(s) concerned or with specific data clarification forms. He/she ensures the completion of the Investigator file and retrieves all documents necessary for updating the trial master file.

When applicable, the CRA may retrieve duplicate of the CRF to be sent to the data management department.

10.2.1.3 Close-out visit

A close out visit will take place after the study has come to a conclusion. The CRA will retrieve all investigational products, auxiliary treatment, materials, CRFs, consent forms (if applicable) and to confirm the completion of the Investigator file, including all study related documents. When necessary, the Sponsor may also ask for the resolution of any delayed queries in the CRFs.

